9.6 Interim Analysis

An interim analysis will be conducted to evaluate the therapeutic equivalence of EPIAO with the standard treatment EPREX after a treatment period of 24 weeks. The analysis will be performed by an independent statistician, who is not involved in the trial conduct other than this interim analysis. The independent statistician will be unblinded and will conduct the analysis using actual treatment assignments. This interim analysis will be conducted after all the randomized patients complete the Visit 16 (Week 36/Day 252). The results of the interim analysis will be communicated to Independent sponsor representative. All other personnel involved in the study will remain blinded. The analysis will be performed in terms of efficacy, safety and immunogenicity between the treatment arms as per the final analysis stated in section 9.

The sponsor of the study wishes to use the data from the interim analysis to plan for registration of EPIAO in other countries where it is yet to be marketed. An interim report will be used to meet the requirement for local registration. A complete analysis will be conducted at the end of the treatment period.

9.7 Safety Monitoring Committee (SMC)

The SMC will consist of 3 doctors independently from the study centers. The SMC will meet at least every 6 months to review the safety data from the study. The SMC can also meet on an ad-hoc basis in case of an occurrence of an SAE.

9.8 Sample Size Determination

A sample size of 112 subjects per group is calculated to achieve a power of more than 80% for proof of equivalence for both co-primary endpoints. Considering 2 stratification factors i.e. body weight (Kg): ≤ 58 , $59-74$ & ≥ 75 , Hb level (g/dl): $10 - 11$ & $> 11 - 12$ and to balance between the two treatment groups in Thailand and Russia, the total number of subjects to be randomized is estimated to be 264 (n=132 subjects in each group) since a drop-out rate of approximately 18% was expected.

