Planned Sample Size:	A sample size of 112 subjects per group is calculated to achieve a power of more than 80% for proof of equivalence for both co-primary endpoints. Considering 2 stratification factors i.e. body weight (Kg): ≤58, 59-74 & ≥75, Hb level (g/dl): 10 – 11 & > 11 – 12 and to balance between the two treatment groups in Thailand and Russia, the total number of subjects to be randomized is estimated to be 264 (n=132 subjects in each group) since a drop-out rate of approximately 18% was expected. The subjects will be randomized into two groups (n=132 subjects in each group) in a 1:1 ratio.
Dosage Form, Dose and Route of Administration of IP:	EPIAO injection will be administrated intravenously one to three times a week at the end of dialysis session for a period of 52 weeks. The maximum allowable dose is 300 IU/kg/week.
Dosage Form, Dose and Route of Administration of comparator:	EPIAO injection will be administrated intravenously one to three times a week at the end of dialysis session for a period of 52 weeks. The maximum allowable dose is 300 IU/kg/week.
Study Endpoints:	
Primary endpoint
 
Mean absolute change in haemoglobin level from baseline to 6 months after treatment with EPIAO/EPREX in parallel groups (g/dl).Mean absolute change in weekly epoetin dosage per kg body weight from baseline to 6 months after treatment with EPIAO/EPREX in parallel groups (IU/kg/week) 
Secondary Endpoints:
 
Proportion of subjects hemoglobin values are within 10 - 12 g/dl for the last 4 weeks of the period for assessment of treatment of efficacy and safety (weeks 32-36)

	
• Proportion of subjects with any haemoglobin measurement outside the target range during the double-blind treatment period• Mean hemoglobin and hematocrit levels every 4 weeks within treatment period (52 weeks)• Mean doses of the study products (IU/kg/week) every 4 weeks throughout the study period (52 weeks)• Incidence of blood transfusions 
Safety endpoints:
 
• Incidence and nature of adverse events• Incidence of drug related adverse events• Clinically significant changes in the vital signs, physical and laboratory examination• Number of subjects who prematurely withdrew from the study due to AE and SAE• Number of subjects with presence of anti-erythropoietin antibodies (anti-EPO Ab)

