4.2.3 Subject Replacement

The subjects who do not complete the study will be considered dropouts and will not be replaced.

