9 STATISTICAL METHODS

9.1 Analysis Sets

Three cohorts will be considered for the analysis: The modified intention-to-treat (mITT) cohort, per protocol (PP) and safety cohort. Per-Protocol cohort population will be considered as primary population for analysis of efficacy.

Modified Intention-to-treat Cohort:

All randomized subjects who receive study medication, have a baseline and at least one post-treatment measurement will be included in the MITT Cohort.

Per-protocol Cohort:

All randomized subjects who complete both the baseline visit and end of treatment visit and who have no major protocol violations will be included in the PP population. Subjects with major protocol violations will be excluded from this cohort.

Detailed description of what constitutes a protocol violation will be defined in the SAP.

Safety Cohort:

All subjects who are randomized at baseline visit will be included in the safety analyses for safety endpoints.

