9.2 General Statistical Considerations

Analysis for all efficacy endpoints using the PP population will be the primary approach for analysis. Secondary analysis will be performed using the mITT population. For safety endpoints using the safety cohort will be the primary approach for analysis.

The SAS® package (SAS® Institute Inc., USA, and Version 9.2 or higher) will be used for statistical evaluation.

Descriptive statistics, such as mean, standard deviation, median, minimum and maximum values will be provided for the continuous variables and the number of observations and percentage will be provided for the categorical variables.

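### Randomising 132 per group does not keep 112 per group at the stated 18% drop-out: about 108 remain, because the figure matches 112 × 1.18 rather than 112 / 0.82

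*Protocol*

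**What the plan says.** Section 9.8 of the protocol gives the target first: "A sample size of 112 subjects per group is calculated to achieve a power of more than 80% for proof of equivalence", and this applies to both co-primary endpoints. It then names two stratification factors (body weight and Hb level) and balance of the arms in Thailand and Russia, and concludes that the total to be randomised "is estimated to be 264 (n=132 subjects in each group) since a drop-out rate of approximately 18% was expected". The Planned Sample Size entry of the synopsis repeats these figures and adds: "The subjects will be randomized into two groups (n=132 subjects in each group) in a 1:1 ratio".

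Four other places decide how many of the 132 count in the analysis:

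- Section 4.2.3: "The subjects who do not complete the study will be considered dropouts and will not be replaced".
- Section 9.2: "Analysis for all efficacy endpoints using the PP population will be the primary approach for analysis".
- Section 9.1 defines the per-protocol (PP) set as "All randomized subjects who complete both the baseline visit and end of treatment visit and who have no major protocol violations".
- Section 9.2.1 rules out imputation of missing efficacy data.

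**The concern.** The 264 is justified by expected drop-out, so 112 must be the number per group that is left after drop-out. If a fraction d is lost, the number to randomise is n / (1 − d), because the loss applies to everyone randomised. Multiplying n by (1 + d) applies the loss only to the smaller target number and always comes out too low. The stated 132 looks like the second calculation.

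The power statement is attached to 112 per group and the protocol gives none for a smaller number. If its own N and drop-out rate deliver fewer than 112, the claim of more than 80% has no stated basis at the size the trial expects to analyse. Nothing elsewhere makes up the difference: drop-outs are not replaced, missing efficacy values are not imputed, and section 3.1.2 stops recruitment at 264. The primary PP set also removes major protocol violators, who come on top of drop-outs if the 18% means drop-out alone, as written.

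**Working it through.** **Inputs** (section 9.8 and synopsis): n = 112 per group required; d = 0.18; N = 132 per group, 264 in total; allocation 1:1. The margin of ±0.5 g/dl for Hb with a 95% confidence interval is from section 9.4.1.

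**1. Reproducing the stated figure.**
- n × (1 + d) = 112 × 1.18 = 132.16, rounded to 132.
- In total: 224 × 1.18 = 264.32, rounded to 264.
- The 20 subjects added are 20/112 = 17.9% of the target, which fits a rate of about 18%.

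**2. Number needed to keep 112.**
- n / (1 − d) = 112 / 0.82 = 136.6, so 137 per group and 274 in total.
- This is 5 per group and 10 in total more than stated.

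**3. Number left from 132.**
- 132 × 0.18 = 23.8 lost; 132 × 0.82 = 108.24, so about 108 remain.
- Shortfall: 112 − 108 = 4 per group (4/112 = 3.6%).
- Loss that 132 can bear: (132 − 112)/132 = 20/132 = 15.2%.

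**4. Does the word for approximately help?** At 17% loss, 132 × 0.83 = 109.6 remain; at 18.5%, 132 × 0.815 = 107.6. Neither reaches 112.

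**5. Effect on power (illustration).** The protocol gives no SD and no assumed true difference, so the power at 112 cannot be reproduced. Assume two one-sided t-tests at 2.5% each, margin 0.5 g/dl, true difference 0, one endpoint only, and an SD chosen so that 112 per group gives the power in the first column:

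| Power at 112 | SD implied (g/dl) | Power at 108 |
|---|---|---|
| 80% | 1.149 | 77.9% |
| 82% | 1.129 | 80.0% |
| 85% | 1.096 | 83.2% |
| 90% | 1.033 | 88.6% |

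Power at 108 therefore stays at 80% or more if power at 112 was at least about 82% (81.4% if the true Hb difference is 0.15 g/dl). For joint power on both endpoints, assumed independent, 80% at 112 becomes about 77.4% at 108, and the break-even is about 82.4%.

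**6. Timing of the loss.** The co-primary endpoints are changes to 6 months, while drop-out is counted over the whole study, with 52 weeks of treatment. If the 18% accrues evenly over those 52 weeks (assumption), the loss from week 13 to Visit 16 at week 36 is 0.18 × 23/52 = 8.0%, and 132 × 0.920 = 121.5, about 121 per group before PP exclusions. If all of it occurs before Visit 16, 108 remain.

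**The case against.** Five points can be made for the plan.

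- **The multiplication by 1.18 is not written down.** Section 9.8 also cites stratification and country balance, and 264 divides evenly into the 3 × 2 × 2 = 12 cells of weight, Hb and country (22 each). This stands as a caution about cause: the multiplication is inferred from the match at both group and total level. The shortfall does not depend on it, since 132 less 18% is about 108 however 132 was reached.
- **Power above 80% is a lower bound.** There may be enough slack at 112 for 108 to stay above 80%. This stands. The protocol gives no way to tell, and a failure of power is not shown.
- **The endpoints are read at 6 months.** Losses after Visit 16 do not remove a 6-month value, and with even accrual the interim equivalence analysis would have about 121 per group, more than 112. This stands as a real limit on the point. The PP definition in section 9.1 nevertheless requires the end of treatment visit, so the final PP set bears the full drop-out plus the exclusions for major violations.
- **The power figures come from a simple model.** They cover one endpoint, with an assumed SD and a zero true difference. They show the order of magnitude only.
- **The gap is small.** Four subjects per group would not change the design. That bears on how serious the error is and does not make the three figures agree.

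**Conclusion.** The concern holds. The target of 112 per group, the 132 per group randomised and the drop-out of about 18% cannot all be right together. At 18% loss about 108 per group remain; 112 are kept only if the loss is at most 15.2%; and keeping 112 at 18% would need 137 per group, 274 in total. This rests only on the protocol's own figures and on reading 112 as the number left after drop-out, which the wording of section 9.8 requires.

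The consequence is modest: 4 evaluable subjects per group, and about 1.5 to 2 points of power on one endpoint under the assumptions above (about 2.6 points jointly, from 80% to 77.4%, if the endpoints are independent). Power at 108 drops below 80% only if power at 112 was under about 82%, which the protocol leaves open. The shortfall applies to a set that requires the end of treatment visit, or to drop-out that happens early; for the Visit 16 analysis it may not arise. The sample-size statement should be corrected, but the error does not by itself show the trial to be underpowered.

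**What to change.** Keep 264 randomised and correct the statement, in section 9.8 and in the Planned Sample Size entry of the synopsis. Suggested text:

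*With 264 subjects randomised (132 per group), 112 evaluable subjects per group are retained for a combined loss from drop-out and per-protocol exclusions of up to about 15%. At a loss of 18%, about 108 per group remain.*

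Add the power at 108 per group for both co-primary endpoints, recomputed by the sponsor from the same SDs and true differences that gave 112.

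The cost is two sentences in two places and one recomputation. No patients are added, and the margins, analysis and conduct stay as they are. The price is a slightly less favourable statement of either the tolerated loss or the power.

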10 DATA INTEGRITY AND QUALITY ASSURANCE

The Investigator/investigational site will permit study-related monitoring, audits, IRB/IEC review and regulatory inspections by providing direct access to source data/documents. Direct access includes permission to examine, analyze, verify, and reproduce any records and reports that are important to the evaluation of a clinical study.

10.1 Study Monitoring Plan

Before the first subject is recruited into the study, the monitor(s) of EAL will visit the selected clinical study facilities to:

- Determine the adequacy of the clinical study facility
- Discuss with the Investigator(s) (and other personnel involved with the study) their responsibilities with regard to protocol adherence and other responsibilities

During the progress of the study, the monitor(s) from EA will have regular contacts with the clinical study facility, including visits at regular intervals to:

- Provide information and support to Investigator(s)
- Confirm the continued adequacy of the clinical study facility
- Confirm that the investigational team is adhering to the protocol, GCP and applicable regulatory requirements
- Perform source data verification (a comparison of the data in the eCRFs with the subject's medical records, and other records relevant to the study).
- Check that the data are being accurately and completely recorded in the eCRFs, and that drug accountability checks are being performed
- Verify the protection of the rights and well-being of the subjects

During these visits, CRFs and supporting documentation related to the study will be reviewed and any discrepancies or omissions or any other issues will be resolved. The monitor or another EA representative will be available between visits if the investigator(s) or other staffs need information or advice.

After each monitoring visit, the monitor will prepare a monitoring report. A follow up letter will be prepared and sent to the investigator for activities done and the resolution plan, if any. These all activities will be as per the current version of EA SOP's.

The Principal Investigator will also ensure that the monitor or other compliance or quality assurance reviewer is given access to all the above noted study-related documents and study related facilities (e.g. pharmacy, etc.), and has adequate space to conduct the monitoring visit.

The Investigator agrees to cooperate with the monitor to ensure that any problems detected in the course of these monitoring visits are addressed and documented.

10.2 Data Collection

The study CRF is the primary data collection instrument for the study. Data will be collected using electronic case report forms (eCRFs) that are specifically designed for this study. The eCRFs are used to record study data and are an integral part of the study and subsequent reports. Therefore, the eCRFs must be completed for each subject screened or enrolled according to the subject's source data. All the eCRF entries should be made according to the instructions given in the investigator's Remote Data Capture (RDC) manual.

If applicable, subjects are to be identified by initials, birth date and subject number. All data requested will be first recorded on the source document and then on the CRF. Data will be entered at the site by the appropriately designated and trained site personnel.

Each entered eCRF must be approved by the site investigator, verified against the subject's source documents by the Clinical Research Associate (CRA)/monitor and reviewed by Data Management prior to locking the database. Once all the eCRFs for a subject have been completed, approved, verified, reviewed and cleaned, the subject's eCRFs will be locked.

10.3 Data Management

Data management will be handled by EA. EA shall ensure that clinical study data collected throughout the trial are complete, accurate and of the highest quality and shall be performed in accordance with applicable ICH guidelines and regulations. All the source documents will be maintained at the study site for audit and monitoring purposes.

Data Management Plan (DMP) shall include all general and study-specific data management processes and will identify the applicable processes, the people responsible for performing it, all relevant SOPs to be used and what is expected as output/ documentation.

CRFs shall be made available to the data management site in electronic format. Clinical data discrepancies will be identified and data queries shall be resolved depending on the type of query as described in the DMP. Types of data to be coded will include, but may not be limited to, adverse events and medications. Adverse events will be coded using the MedDRA (latest version) adverse experience coding dictionary. Medications will be coded using the WHO – DDE (latest version).

Periodic reviews of the safety database and the clinical database will occur to ensure consistency between the databases. The protocol and/or CRFs may be amended after the database and DMP have been approved. If changes to the database structure, database contents, or DMP are needed, appropriate documentation, re-validation and approval will occur as necessary.

All data management documentation collected and stored by EAL during the course of study will be sent to Sponsor at study closeout as determined by the study team. This documentation will include, but is not limited to, subject folders, database specifications, the DMP with any amendments, etc.

Source documentation supporting the CRF data (lab reports for pregnancy test etc.) should indicate the subject's participation in the study and should document the dates and details of study procedures, AEs, and subject status. For subjects who discontinue or terminate from the study, the CRFs will be completed as much as possible, and the reason for the discontinuation or termination clearly and concisely specified on the Study exit Form. All CRFs must be kept current so that they always reflect the latest observations on the subjects participating in the study.

10.4 Study Documentation and Storage

The Investigator will maintain a Signature List of appropriately qualified persons to whom he/she has delegated study duties. All persons authorized to make entries and/or corrections on case report forms will be included on the Signature List.

Source documents are original documents, data, and records from which the subject's case report form data are obtained. These include but are not limited to hospital records, clinical and office charts, laboratory and pharmacy records, diaries, microfiches, X-rays, and correspondence.

The Investigator and study staff are responsible for maintaining a comprehensive and centralized filing system (Trial Master File) of all study-related (essential) documentation, suitable for inspection at any time by representatives from sponsor and/or applicable regulatory authorities.

Essential documents include:

- Subject files containing demographic information, evidence supporting the diagnosis/condition for which the subject is being studied, general information supporting the subject's participation in the study, general history and physical findings, hospitalization or emergency Room records (if applicable), each study visit by date, including any relevant findings/notes by the investigator(s), occurrence (or lack) of AEs, and changes in medication usage, including the date the study drug commenced and completed, any additional visits during the study, any relevant telephone conversations with the subject regarding the study or possible adverse events
- An original, signed informed consent form for study participation and supporting copies of source documentation (if kept).
- Study files containing the protocol with all amendments, Investigator's Brochure, copies of relevant essential documents required prior to commencing a clinical study, and all correspondence to and from the IRB and sponsor.
- Records related to the IP(s) including acknowledgment of receipt at site, accountability records and final reconciliation and applicable correspondence.
- The investigator must also retain all subject specific printouts/reports of tests/procedures performed as a requirement of the study. During monitoring visits the monitor will need to validate data in the eCRFs against these sources of data.

In addition, all original source documents supporting entries in the case report forms must be maintained and be readily available.

During this study, an Investigator is required to prepare and maintain adequate and accurate case histories designed to record all observations and other data pertinent to the investigation on each individual treated with the investigational product or entered as a control in the investigation. Data reported on the eCRF, that are derived from source documents, must be consistent with the source documents or the discrepancies must be explained. In accordance with the applicable regulatory requirement(s), the confidentiality of records that could identify subjects must be protected, respecting the privacy and confidentiality rules.

Essential documents should be retained until at least 2 years after the last approval of a marketing application in an ICH region and until there are no pending or contemplated marketing applications in an ICH region or at least 2 years have elapsed since the formal discontinuation of clinical

development of investigational product. These documents should be retained for a longer period however if required by the applicable regulatory requirements or by an agreement with the sponsor. It is the responsibility of the sponsor to inform the investigator/institution as to when these documents no longer need to be retained.

10.5 Record Keeping

Records of subjects, source documents, monitoring visit logs, inventory of study product, regulatory documents (eg, protocol and amendments, IRB/EC correspondence and approvals, approved and signed informed consent forms, Investigator's Agreement, clinical supplies receipts, distribution and return records), and other sponsor correspondence pertaining to the study must be kept in appropriate study files at the site.

Source documents include all recordings and observations or notations of clinical activities and all reports and records necessary for the evaluation and reconstruction of the clinical study. These records will be retained in a secure file for the period required by the institution or site policy. Prior to transfer or destruction of these records sponsor must be notified in writing and be given the opportunity to further store such records.

In the event of PI withdraws from the study (e.g., relocation, retirement), the records shall be transferred to a mutually agreed upon designee (e.g., another Investigator, IRB). Notice of such transfer will be given in writing to Sponsor.

